9.3.4 Visit 4 (Day 15) or Early Termination

The Visit 4 will be performed on Day 15 or at the Early Termination Visit. The following procedures will be performed and documented:

- Physical examination.
- Vital signs.
- Weight
- Collection of blood and urine samples for hematology, serum chemistry, urine pregnancy testing (if applicable), and urinalysis.
- Inquiry regarding any concomitant medications.
- Inquiry for Adverse Events.
- ECG procedure.
- The investigator will assess: presence of muscle spasm, presence of local pain, limitation of activities of daily living, and limitation of range of motion.
- Physician's clinical global assessment based on presence of muscle spasm, presence of local pain, limitation of range of motion, and limitation of activities of daily living was recorded.
- Subject diary collection and review.
- Unused study drug return and compliance calculation.
- For all subjects receiving study medication, the investigator must complete the End of Study (e)CRF page.

9.3.5 Follow-up call

Follow-up telephone calls will be used to monitor AEs for 3 weeks after the last dose of study drug.

9.3.6 Post Study Care

The study medication will not be available upon completion of the subject's participation in the study. The subject should be returned to the care of a physician and standard therapies as required.

10.0 PRETREATMENT EVENTS AND ADVERSE EVENTS

10.1 Definitions

10.1.1 PTEs

A PTE is defined as any untoward medical occurrence in a clinical investigation subject who has signed informed consent to participate in a study but prior to administration of any study medication; it does not necessarily have to have a causal relationship with study participation.

10.1.2 AEs

An AE is defined as any untoward medical occurrence in a clinical investigation subject administered a drug; it does not necessarily have to have a causal relationship with this treatment.

An AE can therefore be any unfavorable and unintended sign (eg, a clinically significant abnormal laboratory finding), symptom, or disease temporally associated with the use of a drug whether or not it is considered related to the drug.

10.1.3 Additional Points to Consider for PTEs and AEs

An untoward finding generally may:

- Indicate a new diagnosis or unexpected worsening of a pre-existing condition. (Intermittent events for pre existing conditions underlying disease should not be considered PTEs or AEs.)
- Necessitate therapeutic intervention.
- Require an invasive diagnostic procedure.
- Require discontinuation or a change in dose of study medication or a concomitant medication.
- Be considered unfavorable by the investigator for any reason.
- PTEs/AEs caused by a study procedure (eg, a bruise after blood draw) should be recorded as a PTE/AE.

Diagnoses vs signs and symptoms:

- Each event should be recorded to represent a single diagnosis. Accompanying signs (including abnormal laboratory values or ECG findings) or symptoms should NOT be recorded as additional AEs. If a diagnosis is unknown, sign(s) or symptom(s) should be recorded appropriately as a PTE(s) or as an AE(s).

Laboratory values and ECG findings:

- Changes in laboratory values or ECG parameters are only considered to be PTEs or AEs if they are judged to be clinically significant (ie, if some action or intervention is required or if the investigator judges the change to be beyond the range of normal physiologic fluctuation). A laboratory re-test and/or continued monitoring of an abnormal value are not considered an intervention. In addition, repeated or additional noninvasive testing for verification, evaluation or monitoring of an abnormality is not considered an intervention.

- If abnormal laboratory values or ECG findings are the result of pathology for which there is an overall diagnosis (eg, increased creatinine in renal failure), the diagnosis only should be reported appropriately as a PTE or as an AE.

Pre-existing conditions:

- Pre-existing conditions (present at the time of signing of informed consent) are considered concurrent medical conditions and should NOT be recorded as PTEs or AEs. Baseline evaluations (eg, laboratory tests, ECG, X-rays etc.) should NOT be recorded as PTEs unless related to study procedures. However, if the subject experiences a worsening or complication of such a concurrent condition, the worsening or complication should be recorded appropriately as a PTE (worsening or complication occurs before start of study medication) or an AE (worsening or complication occurs after start of study medication). Investigators should ensure that the event term recorded captures the change in the condition (eg, “worsening of...”).
- If a subject has a pre-existing episodic condition (eg, asthma, epilepsy) any occurrence of an episode should only be captured as a PTE/AE if the episodes become more frequent, serious or severe in nature, that is, investigators should ensure that the AE term recorded captures the change in the condition from Baseline (eg “worsening of...”).
- If a subject has a degenerative concurrent condition (eg, cataracts, rheumatoid arthritis), worsening of the condition should only be captured as a PTE/AE if occurring to a greater extent to that which would be expected. Again, investigators should ensure that the AE term recorded captures the change in the condition (eg, “worsening of...”).

Worsening of PTEs or AEs:

- If the subject experiences a worsening or complication of a PTE after starting administration of the study medication, the worsening or complication should be recorded appropriately as an AE. Investigators should ensure that the AE term recorded captures the change in the condition (eg, “worsening of...”).
- If the subject experiences a worsening or complication of an AE after any change in study medication, the worsening or complication should be recorded as a new AE. Investigators should ensure that the AE term recorded captures the change in the condition (eg, “worsening of...”).

Changes in severity of AEs /Serious PTEs:

- If the subject experiences changes in severity of an AE/serious PTE, the event should be captured once with the maximum severity recorded.

Preplanned surgeries or procedures:

- Preplanned procedures (surgeries or therapies) that were scheduled prior to signing of informed consent are not considered PTEs or AEs. However, if a preplanned procedure is performed early (eg, as an emergency) due to a worsening of the pre-existing condition, the worsening of the condition should be captured appropriately as a PTE or an AE. Complications resulting from any planned surgery should be reported as AEs.

Elective surgeries or procedures:

- Elective procedures performed where there is no change in the subject's medical condition should not be recorded as PTEs or AEs, but should be documented in the subject's source documents. Complications resulting from an elective surgery should be reported as AEs.

Insufficient clinical response (lack of efficacy):

- Insufficient clinical response, efficacy, or pharmacologic action, should NOT be recorded as an AE. The investigator must make the distinction between exacerbation of pre-existing illness and lack of therapeutic efficacy.

Overdose:

- Cases of overdose with any medication without manifested side effects are NOT considered PTEs or AEs, but instead will be documented on an Overdose page of the (e)CRF. Any manifested side effects will be considered PTEs or AEs and will be recorded on the AE page of the (e)CRF.

10.1.4 SAEs

An SAE is defined as any untoward medical occurrence that at any dose:

1. Results in DEATH.
2. Is LIFE THREATENING.
 - The term "life threatening" refers to an event in which the subject was at risk of death at the time of the event; it does not refer to an event that hypothetically might have caused death if it were more severe.
3. Requires inpatient HOSPITALIZATION or prolongation of existing hospitalization.
4. Results in persistent or significant DISABILITY/INCAPACITY.
5. Leads to a CONGENITAL ANOMALY/BIRTH DEFECT.
6. Is an IMPORTANT MEDICAL EVENT that satisfies any of the following:
 - May require intervention to prevent items 1 through 5 above.
 - May expose the subject to danger, even though the event is not immediately life threatening or fatal or does not result in hospitalization.
 - Includes any event or synonym described in the Takeda Medically Significant AE List (Table 10.a).

Table 10.a Takeda Medically Significant AE List

Term	
Acute respiratory failure/acute respiratory distress syndrome	Hepatic necrosis
Torsade de pointes / ventricular fibrillation / ventricular tachycardia	Acute liver failure Anaphylaxis

Malignant hypertension	Acute renal failure
Convulsive seizure	Pulmonary hypertension
Agranulocytosis	Pulmonary fibrosis
Aplastic anemia	Confirmed or suspected endotoxin shock
Toxic epidermal necrolysis/Stevens-Johnson syndrome	Confirmed or suspected transmission of infectious agent by a medicinal product
	Neuroleptic malignant syndrome / malignant hyperthermia
	Spontaneous abortion / stillbirth and fetal death

PTEs that fulfill 1 or more of the serious criteria above are also to be considered SAEs and should be reported and followed up in the same manner (see Sections 10.2.2 and 10.3).

10.1.5 Severity of PTEs and AEs

The different categories of intensity (severity) are characterized as follows:

Mild:	The event is transient and easily tolerated by the subject.
Moderate:	The event causes the subject discomfort and interrupts the subject's usual activities.
Severe:	The event causes considerable interference with the subject's usual activities.

10.1.6 Causality of AEs

The relationship of each AE to study medication(s) will be assessed using the following categories:

Related:	An AE that follows a reasonable temporal sequence from administration of a drug (including the course after withdrawal of the drug), or for which possible involvement of the drug cannot be ruled out, although factors other than the drug, such as underlying diseases, complications, concomitant drugs and concurrent treatments, may also be responsible.
Not Related:	An AE that does not follow a reasonable temporal sequence from administration of a drug and/or that can reasonably be explained by other factors, such as underlying diseases, complications, concomitant drugs and concurrent treatments.

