10.1.7 Relationship to Study Procedures

Relationship (causality) to study procedures should be determined for all PTEs and AEs.

The relationship should be assessed as Related if the investigator considers that there is reasonable possibility that an event is due to a study procedure. Otherwise, the relationship should be assessed as Not Related.

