10.2.1.2 PTE and AE Reporting

At each study visit, the investigator will assess whether any subjective AEs have occurred. A neutral question, such as “How have you been feeling since your last visit?” may be asked. Subjects may report AEs occurring at any other time during the study. Subjects experiencing a serious PTE must be monitored until the symptoms subside and any clinically relevant changes in laboratory values have returned to baseline or there is a satisfactory explanation for the change. Non-serious PTEs, related or unrelated to the study procedure, need not to be followed-up for the purposes of the protocol.

All subjects experiencing AEs, whether considered associated with the use of the study medication or not, must be monitored until the symptoms subside and any clinically relevant changes in laboratory values have returned to baseline or until there is a satisfactory explanation for the changes observed. All PTEs and AEs will be documented in the PTE/AE page of the (e)CRF, whether or not the investigator concludes that the event is related to the drug treatment. The following information will be documented for each event:

1. Event term.
2. Start and stop date.
3. Severity.
4. Investigator’s opinion of the causal relationship between the event and administration of study medication(s) (related or not related) (not completed for PTEs).
5. Investigator’s opinion of the causal relationship to study procedure(s), including the details of the suspected procedure.
6. Action concerning study medication (not applicable for PTEs).
7. Outcome of event.
8. Seriousness.

Patient diaries will not be used as a primary means to collect AEs. However, should the investigator become aware of a potential AE through the information collected with this instrument, proper follow-up with the patient for medical evaluation should be undertaken. Through this follow-up if it is determined that an AE not previously reported has been identified, normal reporting requirements should be applied.

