10.2.2 Collection and Reporting of SAEs

When an SAE occurs through the AE collection period it should be reported according to the following procedure:

A Takeda SAE form must be completed, in English, and signed by the investigator immediately or within 24 hours of first onset or notification of the event. The information should be completed as fully as possible but contain, at a minimum:

- A short description of the event and the reason why the event is categorized as serious.
- Subject identification number.
- Investigator’s name.
- Name of the study medication(s)

CONFIDENTIAL

- Causality assessment.

The SAE form should be transmitted within 24 hours to the attention of the contact listed in Section 1.1.

Any SAE spontaneously reported to the investigator following the AE collection period should be reported to the sponsor if considered related to study participation.

Reporting of Serious PTEs will follow the procedure described for SAEs.

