13.1.4.1 AEs

All AEs will be coded by system organ class, high level term, and preferred term using MedDRA. TEAEs are defined as AEs with onset occurring within 30 days (onset date – last date of dose +1≤30) after study drug administration. TEAEs will be summarized by treatment group and dosing frequency by system organ class and preferred term. The following summary tables will be included in the report: summary of TEAEs and drug-related TEAEs, relationship of TEAEs to study drug (related vs. not-related), severity of TEAEs and related TEAEs. Data listings will be provided for all AEs including PTE, TEAEs, AEs leading to study drug discontinuation, and SAEs.

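### Protocol 10.1.6: Related and Not Related are not mutually exclusive, so an adverse event with plausible timing and a reasonable other explanation meets both

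*Protocol*

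**What the plan says.** Section 10.1.6 defines two categories for the relation of an adverse event to study medication.

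- Related opens with "An AE that follows a reasonable temporal sequence from administration of a drug (including the course after withdrawal of the drug), or for which possible". Its second limb covers an event "for which possible involvement of the drug cannot be ruled out, although factors other than the drug" may share responsibility. The two limbs are joined by *or*, so either is enough.
- Not Related is "An AE that does not follow a reasonable temporal sequence from administration of a drug and/or that can reasonably be explained by other factors". The two limbs are joined by *and/or*, so again either is enough.

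The other factors named are the same in both lines: underlying disease, complications, concomitant drugs and concurrent treatments.

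Section 10.2.1.2 records causality as a two-way choice: "Investigator’s opinion of the causal relationship between the event and administration of study medication(s) (related or not related) (not completed for PTEs"). Section 13.1.4.1 then plans a summary of drug-related TEAEs, a table of the "relationship of TEAEs to study drug (related vs. not-related"), and the severity of related TEAEs. Section 10.3.1 makes the sponsor responsible for expedited reporting of suspected unexpected serious adverse reactions.

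For causality to study procedures, section 10.1.7 uses a different construction. A reasonable possibility makes the event Related, and then: "Otherwise, the relationship should be assessed as Not Related".

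**The concern.** A two-category classification needs each event to fall in exactly one category. Here an investigator who sees plausible timing and a reasonable alternative cause can tick either box and be following the protocol.

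The overlap is not confined to rare cases. Appendix E lists drowsiness, dizziness, headache and nausea as frequent reactions. In subjects with acute neck or back pain, such complaints can begin after a dose and still have a sensible explanation in the underlying condition or another medicine.

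About 10 sites will make these judgements (6.1), and no safety or endpoint committee will review them (11.0). The category is fixed when the investigator enters it, so an analysis plan could not later recover a consistent classification. At stake are the drug-related tables that support the safety objective and, for a serious event, whether it counts as a suspected reaction.

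**Working it through.** The protocol states no figure on this point, so there is none to reproduce. The check is one of logic.

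**Inputs, all from 10.1.6.** Let T = reasonable temporal sequence, R = drug involvement cannot be ruled out, O = can reasonably be explained by other factors.

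- Related = T or R
- Not Related = (not T) or O

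**All eight combinations:**

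| T | R | O | Related | Not Related | Result |
|---|---|---|---|---|---|
| yes | yes | yes | met | met | both |
| yes | yes | no | met | – | Related only |
| yes | no | yes | met | met | both |
| yes | no | no | met | – | Related only |
| no | yes | yes | met | met | both |
| no | yes | no | met | met | both |
| no | no | yes | – | met | Not Related only |
| no | no | no | – | met | Not Related only |

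Four combinations meet both definitions, two are Related only, two are Not Related only, and none meets neither. With T and O both true, both definitions are met whatever R is. No rule elsewhere in the protocol says which line takes precedence.

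**With the construction of 10.1.7.** Not Related = not (T or R). The four overlapping rows become Related, giving 4 + 2 = 6 rows Related and 2 Not Related, with no overlap and no gap.

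**Illustration of size (assumed inputs).** The protocol gives no adverse event rates. Assume 36 of 90 subjects in an arm have a TEAE (40%), a share s of those 36 fall in the overlap, and the rest split evenly between the two categories.

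- Lowest related rate = (1 − s) × 36 × 0.5 / 90
- Highest related rate = lowest + s × 36 / 90

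| s | Clearly related | Overlap | Lowest | Highest |
|---|---|---|---|---|
| 10% | 16.2 | 3.6 | 16.2/90 = 18% | 19.8/90 = 22% |
| 25% | 13.5 | 9 | 13.5/90 = 15% | 22.5/90 = 25% |
| 50% | 9 | 18 | 9/90 = 10% | 27/90 = 30% |

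The width of the range is 0.4 × s, that is 4, 10 or 20 percentage points. These figures show scale under the stated assumptions; they do not predict this trial.

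**The case against.** The best defence is that the text already separates the mixed case. Related tolerates other factors that may also be responsible, while Not Related requires that they reasonably explain the event. On a natural reading, Not Related then means explained by something else instead of the drug. Part of this stands: a reader might infer that any conceivable alternative cause puts an event in both categories, and that is too broad. A merely possible alternative leaves the event Related. But the text nowhere says *instead of the drug*. Once the alternative is a reasonable explanation and the timing also fits, both definitions are met as written.

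A second objection is that little depends on the category. Much of this stands too:

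- A reader might infer that serious events could go unreported. The documents do not support that. All adverse events are documented regardless of causality (10.2.1.2), and within the collection period SAEs go to the sponsor whatever the causality opinion (10.2.2).
- The rule for SAEs after the collection period, that they "should be reported to the sponsor if considered related to study participation", might look like another consequence. It refers to participation in the study and not to the drug, so it does not rest on the 10.1.6 definitions.
- A reader might infer that a treatment difference in related events would be lost. Section 13.1.4.1 plans summaries and listings, with no between-arm test or interval for related events. Under the blind, the ambiguity also applies to both arms. The demonstrable problem is the level and reproducibility of the related rate.

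It can also be said that causality is always the investigator's opinion. That is true, but variation in judgement is a different matter from two definitions that permit opposite answers to the same judgement.

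**Conclusion.** The overlap is real and follows from the wording alone: four of the eight logical combinations satisfy both definitions, and nothing resolves them. This is a contradictory rule in the protocol, not detail left to a later document.

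Its reach is limited. It affects the level of the drug-related TEAE rate, the table of TEAEs by relationship and the severity of related TEAEs. It may affect classification as a suspected reaction under 10.3.1, to the extent that this relies on the investigator's causality entry. Total TEAE counts, SAE reporting to the sponsor within the collection period, and all efficacy analyses are untouched.

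The size cannot be derived from the protocol. The ranges of 4, 10 and 20 points rest on an assumed 40% TEAE rate, assumed overlap shares and an even split of the remainder. It is a modest wording defect, worth correcting because it cannot be undone once the data are entered.

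**What to change.** In 10.1.6, keep Related as written and define Not Related as any adverse event that does not meet it, using the same construction as 10.1.7. Put the same rule in the eCRF completion guideline.

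Simply replacing *and/or* by *and* in the Not Related line is not a substitute. An event with no plausible timing, no suspected drug involvement and no identified alternative would then fit neither category, which is a gap the present text does not have.

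The drafting cost is one sentence in each document. The substantive cost is a higher count of related events, because all four overlapping combinations become Related. The rise could be marked: under Related as written, plausible timing alone is enough, and with once-daily dosing for 14 days many on-treatment events will have it. The study report should say so when it presents the drug-related tables.

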10.1.7 Relationship to Study Procedures

Relationship (causality) to study procedures should be determined for all PTEs and AEs.

The relationship should be assessed as Related if the investigator considers that there is reasonable possibility that an event is due to a study procedure. Otherwise, the relationship should be assessed as Not Related.

10.1.8 Start Date

The start date of the AE/PTE is the date that the first signs/symptoms were noted by the subject and/or physician.

10.1.9 Stop Date

The stop date of the AE/PTE is the date at which the subject recovered, the event resolved but with sequelae or the subject died.

10.1.10 Frequency

Episodic AEs/PTE (eg, vomiting) or those which occur repeatedly over a period of consecutive days are intermittent. All other events are continuous.

10.1.11 Action Concerning Study Medication

- Drug withdrawn – a study medication is stopped due to the particular AE.
- Dose not changed – the particular AE did not require stopping a study medication.
- Unknown – only to be used if it has not been possible to determine what action has been taken.
- Not Applicable – a study medication was stopped for a reason other than the particular AE eg, the study has been terminated, the subject died, dosing with study medication was already stopped before the onset of the AE.

